### 5.3 Treatment of subjects

Subjects treated with metformin ± one other OAD (AGI, SU, glinides or TZD) in accordance with the inclusion criterion are eligible for the trial. At randomisation subjects will have to discontinue all OADs except for metformin, leaving this at pre-trial dose in combination with one of the treatments for subcutaneous injection described below:

- 1. IDegLira added to current metformin therapy. Start dose will be 10 dose steps (10 U of IDeg and 0.36 mg of liraglutide) and will be titrated according to the Titration Guideline (appendix A) aiming for a FPG target of 4.0-5.0 mmol/L
- 2. IDeg added to current metformin therapy. Start dose will be 10 U and will be titrated according to the Titration Guideline aiming for a FPG target of 4.0-5.0 mmol/L
- 3. Liraglutide added to current metformin therapy. Start dose will be 0.6 mg and subsequent 0.6 mg weekly dose escalation to the target dose of 1.8 mg. If subjects are not able to tolerate the dose escalation as described above, the visit window may be used to prolong exposure time for a given dose. Liraglutide dose of 1.8 mg/day will be continued for the remaining part of the trial and at each site visit/telephone contact subjects must be asked to confirm their dose

The Titration Guideline contains more detailed guidance on switching from pre-trial treatment to trial products, timing of injection, and titration of these.

| Protocol | Date: 07 October 2014 | Novo Nordisk | Trial ID: NN9068-4148 | CONFIDENTIAL | Status: Final | Final |

Page:

21 of 84

### 5.4 Treatment in the follow-up period

After 26 weeks of trial product exposure, a 1-week interval between the end of treatment (Visit 28) and the follow-up (Visit 29) is necessary to allow for trial product washout. Subjects must at the investigator's discretion be switched to a suitable marketed product excluding insulin detemir (Levemir®), IDeg, or any GLP-1 receptor agonists as these may interfere with antibody measurements performed at Visit 29.

### 5.5 Treatment after end of trial

When completing the trial subjects should be switched to a suitable marketed product at the discretion of the investigator.

### 5.6 Rationale for treatment

Enrolment of insulin-naïve subjects with T2DM, inadequately controlled on 1-2 OADs, has been chosen to demonstrate the efficacy and safety of IDegLira, when added to metformin.

The rationale for including subjects with pre-trial treatment metformin ± one other OAD is to mimic common practice of diabetes treatment in subjects with T2DM failing on 1-2 OADs and will prevent undue heterogeneity of the treatment arms due to diverse treatment. The daily dose of metformin (≥ 1500 mg or max tolerated dose) is close to the maximum recommended dose as per local labelling for the treatment of type 2 diabetes.

When glycaemic control is not achieved or sustained on this background, the addition of another OAD, or initiation of GLP-1 receptor agonists, basal insulin or IDegLira can be considered.

The expected outcome after 26 weeks of treatment with IDegLira compared to IDeg is similar change in HbA1c, less weight gain, lower post-prandial glucose levels, and a lower rate of hypoglycaemic events. In comparison with liraglutide a greater decrease in HbA1c, a lower FPG level and fewer gastro intestinal AEs are anticipated for IDegLira. For more detailed information on IDegLira, please see Investigator's Brochure or any updates hereof.

IDeg and liraglutide have been included as comparators in order to comply with regulatory requirements to assess the risk benefit profile of the combination product as compared to the individual components.

Apart from metformin, other OADs are primarily excluded at randomisation because they are not approved for use combined with liraglutide and metformin by the CFDA and are also not supported by the China clinical programme for liraglutide in terms of safety (and efficacy).

Metformin treatment will be in accordance with locally approved label.

Date: 07 October 2014 | Novo Nordisk Protocol Trial ID: NN9068-4148 Version: 2.0 CONFIDENTIAL UTN: U1111-1154-6671 Final Status: 22 of 84

Page:

#### **Trial population** 6

#### 6.1 Number of subjects

Countries planned to participate: China

Number of subjects planned to be screened: 1200

Number of subjects planned to be randomised: 720

Number of subjects expected to complete the trial: 612

A screening failure rate of 40% and a withdrawal rate of 15% are anticipated.

#### 6.2 Inclusion criteria

For an eligible subject, all inclusion criteria must be answered "yes".

- 1. Informed consent obtained before any trial-related activities. Trial-related activities are any procedures that are carried out as part of the trial, including activities to determine suitability for the trial
- 2. Male or female, age  $\geq 18$  years at the time of signing informed consent
- 3. Type 2 diabetes mellitus (clinically diagnosed)
- 4. HbA1c 7.0-10.0 % (both inclusive) by central laboratory analysis, with the aim of a median of 8.3%. When approximately 50% of the randomised subjects have a HbA1c above 8.3%, the remaining subjects randomised must have a HbA1c below or equal to 8.3%; or when approximately 50% of the randomised subjects have a HbA1c below or equal to 8.3%, the remaining subjects randomised must have a HbA1c above 8.3%
- 5. Current treatment for at least 90 calendar days prior to screening with metformin  $\pm$  one other OAD: AGI, SU, glinides or TZD. For  $\geq$  60 calendar days prior to screening subjects should be on a stable dose of:
  - a. Metformin (≥1500 mg or max tolerated dose) or
  - b. Metformin (≥1500 mg or max tolerated dose) and SU (≥half of the max approved dose according to local label) or
  - c. Metformin (≥1500 mg or max tolerated dose) and glinides (≥half of the max approved dose according to local label) or
  - d. Metformin (≥1500 mg or max tolerated dose) and AGI (≥half of the max approved dose according to local label) or
  - e. Metformin (≥1500 mg or max tolerated dose) and TZD (≥half of the max approved dose according to local label)
- 6. Body mass index (BMI)  $\leq 40 \text{ kg/m}^2$

Protocol Trial ID: NN9068-4148		Date: Version:	07 October 2014 2.0	Novo Nordisk
UTN: U1111-1154-6671	CONFIDENTIAL	Status:	Final 23 of 84	

7. Able and willing to adhere to the protocol including performing self-monitoring of plasma glucose profiles, keeping a trial diary and using a pre-filled pen device

### 6.3 Exclusion criteria

For an eligible subject, all exclusion criteria must be answered "no".

- 1. Known or suspected hypersensitivity to trial product(s) or related products
- 2. Previous participation in this trial. Participation is defined as informed consent
- 3. Female who is pregnant, breast-feeding or intends to become pregnant or is of child-bearing potential and not using adequate contraceptive methods (sterilisation, intrauterine device (IUD), oral contraceptives or barrier methods)
- 4. Receipt of any investigational medicinal product within 30 calendar days prior to Visit 1
- 5. Current use of any antidiabetic drug (except for metformin, AGI, SU, glinides or TZD) or anticipated change in concomitant medication, that in the investigator's opinion could interfere with glucose level (e.g. systemic corticosteroids)
- 6. Use of non-herbal Chinese medicine or other non-herbal local medicine with unknown/unspecified content within 90 calendar days prior to screening. Herbal traditional Chinese medicine or other local herbal medicines may, at the investigator's discretion, be continued throughout the trial
- 7. Treatment with insulin (except for short-term treatment at the discretion of the investigator)
- 8. Treatment with GLP-1 receptor agonists or DPP-4 inhibitors within 90 calendar days prior to screening
- 9. Impaired liver function, defined as alanine aminotransferase (ALAT) ≥ 2.5 times upper normal range (UNR)
- 10. Impaired renal function defined as serum-creatinine  $\geq 133~\mu mol/L$  for males and  $\geq 125~\mu mol/L$  for females, or as defined according to local contraindications for metformin
- 11. Screening calcitonin ≥ 50 ng/L
- 12. Personal or family history of medullary thyroid carcinoma (MTC) or multiple endocrine neoplasia type 2 (MEN2)
- 13. Cardiac disorder defined as: congestive heart failure (NYHA class III-IV), diagnosis of unstable angina pectoris, cerebral stroke and/or myocardial infarction within the last 12 months prior to screening and/or planned coronary, carotid or peripheral artery revascularisation procedures
- 14. Severe uncontrolled treated or untreated hypertension (systolic blood pressure ≥ 180 mm Hg or diastolic blood pressure ≥ 100 mm Hg
- 15. Proliferative retinopathy or maculopathy (macular oedema), requiring acute treatment
- 16. Subject with a clinically significant, active (during the past 12 months) disease of the gastrointestinal, pulmonary, neurological, genitourinary or haematological system (except for conditions associated with T2DM) that in the opinion of the investigator may confound the results of the trial or pose additional risk in administering trial drug

Protocol Trial ID: NN9068-4148 UTN: U1111-1154-6671	CONFIDENTIAL	Date: Version: Status:	07 October 2014 2.0 Final	Novo Nordisk
		Page:	24 of 84	İ

- 17. Mental incapacity, unwillingness or language barrier precluding adequate understanding of the trial procedure or cooperation with the trial site personnel
- 18. Known or suspected abuse of alcohol or narcotics
- 19. History of pancreatitis (acute or chronic)
- 20. Suffer from a life threatening disease including malignant neoplasms and medical malignant neoplasms within the last 5 years (except basal and squamous cell skin cancer)

### 6.4 Withdrawal criteria

The subject may withdraw at will at any time without explanation.

The subject may be withdrawn from the trial at the discretion of the investigator due to a safety concern or if judged non-compliant with trial procedures

A subject must be withdrawn if the following applies:

- 1. Inclusion in the trial in violation of the inclusion and/or exclusion criteria
- 2. Pregnancy
- 3. Intention of becoming pregnant
- 4. Initiation of any systemic treatment with products which in the investigator's opinion could interfere with glucose metabolism (e.g. systemic corticosteroids)
- 5. If all pre-breakfast SMPG values taken on three consecutive days or if any FPG samples analysed by the central laboratory exceeds the limit of:
  - 15.0 mmol/L after baseline to week 6
  - 13.3 mmol/L from week 6 to week 12
  - 11.1 mmol/L from week 12 to last week prior to end of treatment
  - and given there is no intercurrent cause for the hyperglycaemia, a confirmatory FPG must be performed at the next scheduled visit, or if deemed necessary by the investigator at an unscheduled visit. If the confirmatory FPG exceeds the limits stated above, the subject must be withdrawn
- 6. If the investigator suspects acute pancreatitis, all drugs suspected to relate to this condition should be discontinued until confirmatory tests have been conducted and appropriate treatment should be initiated. Subjects who are diagnosed with acute pancreatitis with minimum 2 of 3 characteristics: abdominal pain, amylase and/or lipase > 3x UNR or characteristic findings on computer axial tomography (CT)/magnetic resonance imaging (MRI) must be withdrawn from the trial

### 6.5 Subject replacement

Subjects who are withdrawn will not be replaced.

Protocol		Date:	07 October 2014	Novo Nordisk
Trial ID: NN9068-4148	CONFIDENTIAL	Version:	2.0	
UTN: U1111-1154-6671	CONFIDENTIAL	Status:	Final	
		Page:	25 of 84	

#### 6.6 Rationale for trial population

The rationale for this specific trial population is to ensure inclusion of subjects resembling the target population in common practice. The HbA1c range is chosen to include subjects for whom diabetes is not optimally controlled on their current treatment and hence would benefit from an intensified treatment regimen.

A BMI limit of  $\leq 40 \text{ kg/m}^2$  is chosen to include as broad a population as possible while excluding morbidly obese individuals who are extremely insulin resistant.

Only serious concomitant conditions i.e. NYHA class III-IV (see appendix C), history of recent serious cardiac event, neoplastic disease, renal or hepatic impairment, major surgery etc.), which could interfere with trial schedule/procedures, preclude subjects from entering into the trial.

#### 7 **Milestones**

Planned duration of recruitment period (First Subject First Visit - Last Subject First Visit): 54 weeks. End of trial is defined as Last Subject Last Visit.

Recruitment will be performed according to an agreement made up-front with the individual investigational site. The screening will be monitored closely during the entire recruitment period. In order to secure recruitment timelines, the agreed distribution of subjects between sites may be changed. The screening and randomisation rate will be followed closely in order to estimate when to stop screening. Please see section 11 for randomisation procedure.

### **Trial registration:**

Information of the trial will be disclosed at clinicaltrials.gov, chinadrugtrials.org.cn and novonordisk-trials.com. According to the Novo Nordisk Code of Conduct for Clinical Trial Disclosure, it will also be disclosed according to other requirements such as those of the International Committee of Medical Journal Editors (ICMJE), the Food and Drug Administration Amendment Act (FDAAA), European Commission Regulation for European Drug Regulatory Authorities Clinical Trials (EudraCT) and other relevant recommendations or regulations. If a subject requests to be included in the trial via the Novo Nordisk e-mail contact at these web sites, Novo Nordisk may disclose the investigator's contact details to the subject. As a result of increasing requirements for transparency, some countries require public disclosure of investigator names and their affiliations.

Page:

26 of 84

### 8 Methods and assessments

### 8.1 Visit procedures

Timing of site visits, telephone contacts, their windows and assessments to be performed are specified in the flow chart in section  $\underline{2}$ . In the following section instructions on how to perform and record results of all assessments are described in more detail.

The investigator must keep a subject screening log, a subject identification code list and a subject enrolment log. The screening log and enrolment log may be combined into one list.

### 8.1.1 Fasting requirement for blood sampling and body weight

As outlined in the flow chart subjects must attend most of the site visits fasting, i.e. at least eight hours without food and drink intake, except for water. Trial products and metformin should be withheld on the day of the site visit until blood sampling and body weight assessment (if applicable) have been performed. Any other prescribed medication should be taken as usual. If the subjects attend the visit in a non-fasting state the blood sampling should be rescheduled as per section 8.1.7.

Please see section 8.1.6 for special requirement in relation to fasting and administration of insulin prior to the follow-up Visit 29.

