## 2 Flow chart

6																	
Screening (SC) Randomisation (R)																	
Site visit (V)																	
Telephone contact (T)																	
Follow-up visit (FU)	SC	R	V	V	T	V	T	V	T	V	T	V	T	V	T	V	FU
Visit number															23 24		
							7		11		15		19		25		
			2		_		8	10	12	1,4	16	10	20	22	26	20	20
Time of visit (week)	1	2	3	4	5	6	9	10	13	14	17	18	21	22	27	28	29
Time of visit (week)	1						5		9		13		17		22		
	-21	0	1	2	3	4	6	8	10	12	14	16	18	20	23	26	27
							7		11		15		19		24 25		
Visit window (days)			±3	±3	±3	±3	±3	±3	±3	±3	±3	±3	±3	±3	±3	±3	+3
Subject related information/a	ssessn	nents															
Informed consent	X																
In/exclusion criteria	X	X															
Randomisation		X															 
Withdrawal criteria			X	X	X	X	X	X	X	X	X	X	X	X	X	X	
Concomitant illness/Medical	X																 
history																	 
Concomitant medication	X	X	X	X	X	X	X	X	X	X	X	X	X	X	X	X	 
Smoking habits	X															X	 
Demography	X																
Diagnosis of diabetes	X																
Diabetes treatment history	X																
Diabetes complications	X																
Family history of diabetes	X																
Body measurements																	
Height	X																
Body weight	X	X				X		X		X		X		X		X	
Waist circumference		X								X						X	
BMI	X															X	
EFFICACY	1		1	ı		ı											
Glucose metabolism																	 
HbA 1c	X	X				X		X		X		X		X		X	 
Fasting plasma glucose		X				X		X		X		X		X		X	-
Fasting insulin		X								X						X	 
Fasting Glucagon		X								X						X	<del>                                     </del>
Fasting C-peptide			v	V	-	V		v	-			V		V	-	X	├
PK Sampling 		X	X	X		X	-	X		X		X		X		X	
Self-measured plasma glucose		-	37	37	37	37	37	37	37	37	37	37	37	37	37	37	₩
1-point SMPG profile		L	X	X	X	X	X	X	X	X	X	X	X	X	X	X	 
9-point SMPG profile		X			L			L	L	X				L	L	X	 
SAFETY Adverse events	X	X	X	X	X	X	X	X	X	X	X	X	X	X	X	X	X
Technical complaints	Λ	X	X	X	X	X	X	X	X	X	X	X	X	X	X	X	Λ
recinical compianits	1	Λ	Λ	Λ	Λ	Λ	Λ	Λ	Λ	Λ	Λ	Λ	Λ	Λ	Λ	Λ	1

| Protocol | | Date: 07 October 2014 | Novo Nordisk | UTN: U1111-1154-6671 | CONFIDENTIAL | CONFIDENTIAL | CONFIDENTIAL | Page: 13 of 84 | CONFIDENTIAL | CONFIDENTIAL | CONFIDENTIAL | Page: 13 of 84 | CONFIDENTIAL |

Canagaina (CC)														1			
Screening (SC) Randomisation (R)																	
Site visit (V)																	
Telephone contact (T)																	

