Follow-up visit (FU)	SC	R	V	V	T	V	T	V	T	V	T	V	T	V	T	V	FU
Visit number															23		
							7		11		15		19		24 25		
							8		12		16		20		26		
	1	2	3	4	5	6	9	10	13	14	17	18	21	22	27	28	29
Time of visit (week)															21		
	-21		,	_	2		5 6		9	10	13	1.0	17	20	22	26	27
	-2	0	1	2	3	4	7	8	10 11	12	14 15	16	18 19	20	23 24	26	27
							_ ′		11		13		17		25		
Visit window (days)			±3	±3	±3	±3	±3	±3	±3	±3	±3	±3	±3	±3	±3	±3	+3
Hypoglycaemic episodes		X	X	X	X	X	X	X	X	X	X	X	X	X	X	X	X
ECG 	X															X	
Eye examination 5	X															X	
Physical examination	X															X	
Vital signs	X	X								X						X	
Antibodies		X								X						X	X
Biochemistry	X	X								X						X	
Haematology	X	X								X						X	
Hormones, calcitonin	X	X								X						X	
Lipids		X								X						X	
Urine dipstick		X								X						X	
Pregnancy test (blood sample)	X															X	
REMINDERS						•	•	•			•		•	•			
Handout ID card	X																
Handout and instruct in BG-meter use	X																
Attend visit fasting		X				X		Х		X		X		X		X	x 
IV/WRS call	X	X				X		X		X		X		X		X	Λ
Dispense trial product. Instruct																	<del>                                     </del>
and hand out Directions for Use.		X				X		X		X		X		X			
Drug accountability		X				X		X		X		X		X		X	
Handout and instruct in/collect diary	X	X	X	X		X		X		X		X		X		X	X
Collect first date and dose of trial			X														
Product  Collect last date and dose of trial		 	 	 	 				 							v	
product																X	
Confirmation of unchanged dose of metformin			X	X	X	X	X	X	X	X	X	X	X	X	X	X	
For liraglutide arm:																	
Confirmation of unchanged dose						X	X	X	X	X	X	X	X	X	X	X	
of liraglutide 																	
End of trial and sign off on case																	X
book	1	1	1	1	1	l	l	l	1	1	L		L	L			Щ

- 1. Screening must take place within 14 calendar days prior to randomisation.
- 2. For source data to be recorded in subject's diary prior to every PK sampling visit, please see section 8.3.4.
- 3. For IDeglira and IDeg arm: Daily pre-breakfast SMPG, last dose prior to titration and dose to be taken after titration must be recorded. For liraglutide arm: Pre-breakfast SMPG on 3 consecutive days prior to each visit/telephone contact must be recorded.

Protocol		Date:	07 October 2014	Novo Nordisk
Trial ID: NN9068-4148	CONFIDENTIAL	Version:	2.0	
UTN: U1111-1154-6671	CONFIDENTIAL	Status:	Final	
		Page:	14 of 84	

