### 8.1.2 Screening (Visit 1)

Must take place within 14 calendar days prior to randomisation.

Before screening, the trial site staff must provide the subjects with oral and written information about the trial. See section 18.1 for instructions on informed consent. Ensure subject has signed the informed consent before any trial related procedures can take place.

At screening, subjects will be assigned a unique number. This will remain the same throughout the trial. The number will be registered in an interactive voice/web response system (IV/WRS) which will be used for screening, randomisation and allocation of trial product to each subject throughout the trial (see section 9.4 and 10 for use of the IV/WRS). Subject numbers will automatically be transferred into an electronic case report form (eCRF) system used by the investigator or other relevant trial site staff for transcription of source data throughout the trial. See section 13 for more information on the eCRF.

At screening subjects will be provided with a card stating that they are participating in a trial and giving contact address(es) and telephone number(s) of relevant trial site staff. Subjects should be instructed to return the card to the investigator at the last trial visit or to destroy the card after the last visit.

Protocol Trial ID: NN9068-4148 UTN: U1111-1154-6671	CONFIDENTIAL	Date: Version: Status:	07 October 2014 2.0 Final	Novo Nordisk
		Page:	27 of 84	

All inclusion/exclusion criteria must be reviewed and if any of the criteria cannot be assessed e.g. criteria related to results from blood sampling performed at screening or if a valid eye examination is missing, the investigator must ensure these are obtained for assessment of eligibility prior to being able to randomise the subject at Visit 2. If the subject is ineligible, please see section 8.1.3 for how to screen fail subjects.

Eligible subjects should be instructed to continue on their current OAD treatment until Visit 2.

Subjects will be provided with diaries for completion of source data in between site visits. Please see section 8.6 for source data to be recorded in the diaries and how review is to be done by the investigator.

Subjects will be provided with a BG-meter for use throughout the trial. Please see section 8.2.12 for instructions.

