### 8.1.4 Randomisation (Visit 2)

All inclusion/exclusion criteria and results from assessments at the screening visit including blood sampling, ECG and eye examination results must be available and reviewed by the investigator prior to randomisation to ensure subject remains eligible.

To be randomised, subjects must discontinue any OAD treatment except for metformin. Subjects will then be randomised to receive IDegLira, IDeg or liraglutide all in combination with metformin. Please see the Titration Guideline for initiation of randomised treatment. Also start doses and titration of IDegLira and IDeg can be found here. Please see section 5.3 for start dose and escalation

Protocol Trial ID: NN9068-4148 UTN: U1111-1154-6671	CONFIDENTIAL	Date: Version: Status:	07 October 2014 2.0 Final	Novo Nordisk
		Page:	28 of 84	

of liraglutide. Subjects must be trained in correct use of the pens, and directions for use of the pens must be provided in writing to randomised subjects. This must be documented in subjects' records. At Visit 2, prior to leaving the site, subjects should demonstrate to the investigator, that they are able to use the pens correctly". The training can be repeated if deemed necessary.

The dose of metformin should remain unchanged throughout the trial. See section 8.2.6.

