### 8.2.14 Hypoglycaemic episodes

Plasma glucose should always be measured and recorded when a hypoglycaemic episode is suspected.

All plasma glucose values:

- $\leq 3.9 \text{ mmol/L or}$
- > 3.9 mmol/L when they occur in conjunction with hypoglycaemic symptoms,

should be recorded by the subject. These must be transcribed into the eCRF on the hypoglycaemic episode form throughout the trial from Visit 2 to Visit 29.

The record should include the following information:

- Date and time of hypoglycaemic episode
- The plasma glucose level before treating the episode (if available)
- Whether the episode was symptomatic
- Whether the subject was able to treat him/herself
- Date, time and dose of last trial product (OR other anti-diabetic treatment) administration prior to episode
- Type of last trial product (OR other anti-diabetic treatment) prior to episode
- Date and time of last main meal prior to episode
- Whether the episode occurred in relation to physical activity
- Any sign of fever or other disease
- Whether the subject was asleep when the episode occurred
- Whether the symptoms of the episode woke up the subject

The answer to the question: "Was subject able to treat him/herself?" must be answered "No" for an episode requiring assistance of another person to actively administer carbohydrate, glucagon, or

Protocol Trial ID: NN9068-4148 UTN: U1111-1154-6671	CONFIDENTIAL	Date: Version: Status:	07 October 2014 2.0 Final	Novo Nordisk
		Page:	35 of 84	

take other corrective actions. Plasma glucose concentrations may not be available during an event, but neurological recovery following the return of plasma glucose to normal is considered sufficient evidence that the event was induced by a low plasma glucose concentration 11.

If the question "Was subject able to treat him/herself?" is answered "No", the following information should be recorded and transcribed into the eCRF:

- Who assisted in the treatment of the hypoglycaemic episode (i.e. family/friend/co-worker or similar, paramedic, doctor or other, please specify)
- Where the treatment was administered (i.e. at home/at friends/at work or similar, in an ambulance, emergency room/hospital or other, please specify)
- Type of treatment provided by other person (i.e. oral carbohydrates, glucagon, IV glucose or other, please specify)
- Were symptoms alleviated by the administration of treatment?

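### Before the baseline fasting draw at Visit 2, section 8.1.1 holds back only trial products and metformin, so a pre-trial add-on OAD may be taken first

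*Protocol*

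**What the plan says.** Protocol section 8.1.1 requires a fast of at least eight hours, water only, at most site visits. It names two items to hold back on the day until blood and body weight have been taken: trial products and metformin. For everything else it says: "Any other prescribed medication should be taken as usual."

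Inclusion criterion 5 (section 6.2) admits subjects on metformin alone or on metformin plus one of a sulphonylurea (SU), glinide, α-glucosidase inhibitor (AGI) or thiazolidinedione (TZD). Three places deal with the end of the add-on drug:

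- Section 8.1.2: "Eligible subjects should be instructed to continue on their current OAD treatment until Visit 2."
- Section 5.3: "At randomisation subjects will have to discontinue all OADs except for metformin."
- Section 8.1.4: "To be randomised, subjects must discontinue any OAD treatment except for metformin."

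In the flow chart, the reminder row "Attend visit fasting" is marked at Visit 2. The row "Fasting plasma glucose" has its first mark there too, as do fasting insulin and fasting glucagon. None of the three is drawn at screening.

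Section 8.2.13 has a broader rule for the home 9-point profile, done in the week before Visits 2, 14 and 28. There, anti-diabetic medication in general is held until the pre-breakfast reading has been taken.

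**The concern.** The rule in 8.1.1 suits the visits after randomisation, when metformin and trial product are the only planned anti-diabetic drugs. At Visit 2 no trial product has been given, so the rule in effect holds back metformin alone and leaves the add-on OAD to be taken as usual. Whether a subject doses before the draw then depends on habit: on waking, or with breakfast.

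The Visit 2 values have no substitute. The baseline rule in section 17 falls back on a screening value only where the assessment was also made at screening, which is not so for these three.

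An affected sample could not be reliably identified later. Section 8.2.6 collects start and stop dates of concomitant medication, not clock times. The hypoglycaemia form in section 8.2.14 does ask for "Date, time and dose of last trial product (OR other anti-diabetic treatment) administration prior to episode," but only for subjects who have an episode.

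At stake are the consistency of baseline FPG, fasting insulin, fasting glucagon and HOMA-β, and a small avoidable hypoglycaemia risk from a glucose-lowering dose on an empty stomach.

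**Working it through.** The protocol gives no figure on this point, so there is none to reproduce. The check sets the sections side by side and then works out how any effect would scale.

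**1. Which draws are exposed.** The flow chart marks fasting attendance at Visits 2, 6, 10, 14, 18, 22 and 28, which is 7 visits (Visit 29 has its own two-hour rule). FPG is drawn at the same 7. Fasting insulin and glucagon are drawn at Visits 2, 14 and 28. Only Visit 2 precedes the stop of the add-on OAD. Exposed draws are therefore 1 of 7 for FPG and 1 of 3 for insulin and glucagon, and in each case the exposed draw is the baseline.

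**2. Whether any text closes the gap.** Section 8.1.2 gives an end point of Visit 2 without saying whether that morning's dose is included. Sections 5.3 and 8.1.4 place the stop at randomisation, which occurs during Visit 2. Section 8.2.13 covers the home reading only. None of the amendment texts shown describes a change to this rule.

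**3. Scale for baseline FPG.** Let p be the share of all randomised subjects who dose before the draw, and d the acute fall in FPG in those subjects. The protocol gives neither.

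- Shift in mean baseline FPG = p × d.
- p = 0: shift = 0.
- p = 1% (0.01 × 720 = 7.2 subjects) and d = 1 mmol/L: 0.01 × 1 = 0.01 mmol/L.
- The relation is linear. Ten times that share (72 subjects) with the same d gives 10 × 0.01 = 0.10 mmol/L.

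These values of p and d are assumptions that show the scaling; they are not estimates. A lower baseline makes the within-arm fall in FPG look smaller by the same p × d.

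**4. Scale for HOMA-β in one affected subject.** Section 17.4.2.1 defines it as 20 × insulin / (FPG − 3.5). Hold insulin fixed and lower FPG by 0.1 mmol/L:

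- Assumed FPG 8 mmol/L: 4.5 / 4.4 = 1.023, a rise of 2.3%.
- Assumed FPG 10 mmol/L: 6.5 / 6.4 = 1.016, a rise of 1.6%.

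Any acute change in insulin is not included.

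**5. Between-arm effect.** The draw precedes any randomised treatment. Randomisation is stratified by previous OAD treatment (section 11), and the standard ANCOVA includes it as a factor (section 17). Dosing first is thus balanced across arms in expectation, and the expected between-arm bias is 0.

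**The case against.** The strongest case on the other side is lack of consequence. The size cannot be derived and may be zero. Only subjects on an add-on OAD, chiefly an SU or glinide, who also dose before the draw could matter; metformin-only subjects cannot be affected. Supportive efficacy endpoints are reported as treatment differences. Fasting insulin, glucagon and HOMA-β are analysed as values after 26 weeks, so their baselines enter only as covariates. All of this stands, and it keeps the point small.

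A second argument is that 8.1.2 can be read as ending the add-on before the Visit 2 morning, and that 8.1.4 makes stopping a condition of randomisation. That reading is possible. But 8.1.1 gives the only general instruction for the morning of a fasting visit, and it points the other way. Sites could reasonably act differently.

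Third, the text shown is version 2.0. Amendment 1 updated section 8 without reproducing all the new wording, and section 8.3 leaves sampling procedures to a laboratory manual. A later text may have closed the gap, and this cannot be settled from what is shown. Stop dates would also partly show who could have dosed on the day.

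On safety, subjects have HbA1c of at least 7.0%, carry a glucose meter and are on their way to the site. The risk is small. Section 8.2.14 has low readings recorded on the episode form ("These must be transcribed into the eCRF on the hypoglycaemic episode form throughout the trial from Visit 2 to Visit 29"), but that does not show added risk.

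A reader might also infer that the FPG or HOMA-β treatment comparisons are biased, or that the carried-over effect of the add-on OAD at baseline is itself a flaw. The documents support neither. The first fails on step 5 above. On the second, subjects are meant to be on their pre-trial treatment at baseline; only the uncontrolled dose that morning is in question.

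**Conclusion.** The gap is real on the text shown: followed literally, 8.1.1 permits an add-on OAD dose in a fasted subject before the only baseline FPG, fasting insulin and fasting glucagon sample. Its size is unknown and probably small. It adds noise to these baselines and may slightly shift within-arm FPG change. The primary endpoint (HbA1c) and the confirmatory endpoints (body weight and hypoglycaemic episodes over 26 weeks of treatment) are not affected. The hypoglycaemia risk is small and avoidable.

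This rests on two assumptions: that 8.1.1 was not reworded in a later version, and that at least some SU or glinide users take the morning dose before attending. It is an optional clarification, worth making because section 8.2.13 already applies the broader rule to the home reading in the same baseline week, and because an affected sample cannot be repaired afterwards.

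**What to change.** In the 8.1.1 sentence that names trial products and metformin, add a third item: any other anti-diabetic medication (including pre-trial OADs at Visit 2). Leave the rest of that sentence as it stands, so that drugs are held only until sampling and, where applicable, weighing are done. Keep the following sentence on other prescribed medication unchanged.

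Make no change to 8.1.2. Requiring the last add-on dose on the day before Visit 2 would stop the drug before eligibility is confirmed at that visit, and would conflict with holding it only until sampling.

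The cost is one amended sentence and a line of site training, with no new visit, sample or eCRF field. A subject who turns out not to be randomised takes one OAD dose a little later. For a randomised subject the held dose is in practice skipped, because the drug stops at randomisation; trial product starts that day or the next (Appendix A, section 2).
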